The evaluation of the Parent Navigation NICU to home program will use a randomized trial design. We will do so by recruiting a population of parents who have an infant in the Children's National NICU, half of whom will receive enhanced usual care by provision of a NICU care notebook and half of whom will receive the same enhanced care- including care notebook- plus Parent Navigation (intervention). All will be patients in the NICU who are discharged from the CNMC NICU. Group assignment will be by randomization, stratified by birth weight (≤ 1500 grams or >1500 grams). The design incorporates extensive measurement of baseline attributes to assess the comparability of intervention and enhanced control groups at inception.

We aim to enroll $n=300$ parents of infants receiving care in the Children's National NICU who are discharged from the CNMC NICU. CNMC has a Level IV NICU which receives a large number of complex cases. To allow for generalization of study findings to other NICUs and other centers, we will enroll all patients discharged from the CNMC NICU.

Study personnel will identify eligible NICU patients by reviewing NICU census data or through the use of the PowerTrials Prescreening function. PowerTrials is a HIPAA-compliant application that is integrated into the Children's National Cerner electronic medical records system (PowerChart). Study inclusion and exclusion criteria will be used to create a Prescreening Rule. A screening engine in PowerChart will compare the criteria to patient data within the medical records system, and a list of potential study subjects will be generated.

Research study staff will approach parents anticipating discharge within 1-2 weeks to invite their participation and, as appropriate, obtain informed consent. If parents of eligible patients are not available, we may contact a parent by phone to set up a time to discuss the study in person. We will obtain in person signatures of consent as appropriate before enrolling potential participants in the study. Recruitment will continue in this fashion until the required sample is enrolled.

Inclusion criteria include:

NICU patients discharged from the CNMC NICU. One parent participant per NICU patient will be identified and enrolled as the participant.

Exclusion criteria include:

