Exclusion criteria include if the infant is not being discharged with a custodial parent (e.g., in custody of Child Protection Services), neither parent can complete an interview in English, the parent who will be providing most of the care is younger than 18 years of age, or the parent/caregiver has plans to leave the DC metropolitan area permanently within the following year.

We are limiting the sample to parents of NICU patients that are >18 years of age, because we are interested in adult behavior and concerns. There are no exclusions based on ethnicity or gender; however, all participants will need to be able to complete the interviews in English. We will selectively enroll the one parent/guardian of infants with the most proficient grasp of English. We do not anticipate that this will limit our inclusion of Hispanic families. Upon review of the past 6 months of NICU discharges, 11% report Hispanic ethnicity. Among those- 92% speak English and only 8% speak Spanish and no English.

Study Design and Data Collection:

Following consent and enrollment, the baseline interview will be conducted in person while the infant is still in the NICU. To assure a consistent methodology for collecting subsequent data, all subsequent interviews will be conducted by telephone after NICU discharge. Participants will complete a short semi-structured interview and a questionnaire of measures detailed below at each time point (see data collection sheets and phone script in documents section). Items and instruments were carefully selected to minimize participant burden. All participants will be interviewed and complete instruments at enrollment and 1 week; 1 month; 3 months; 6 months; and 12 months post NICU discharge.

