Participants will be reimbursed for their participation in data collection. Compensation will be \$20 per each data collection time point and \$50 for in person developmental assessment by [name] (Co-I) in Developmental Clinic at age 12-15 months. Our previous experience with longitudinal research in this population suggests that this amount provides adequate incentive without being coercive.

Infant health outcomes:

Infant health outcomes will include health care utilization (ED visits, hospitalizations, specialty visits, primary care visits) and immunization status.

- Health care utilization:

At each interview, parents will provide information about ED visits, hospitalizations, specialty visits, and primary care visits during the period since the prior interview. All parents/participants will be provided with a calendar to keep track of these encounters for easy recall. We will measure the total number of ED visits, hospitalizations, specialty visits, and primary care visits during the 12 month follow-up period post NICU discharge.

- Immunization status is a frequent measure for use of preventive medical care services and is easily verifiable. We will use receipt of vaccines between NICU discharge and 12 months of age as the outcome measure. We will consider receipt of 3 diphtheria-tetanus acellular pertussis (DTaP) vaccines, 3 Hemophilus influenzae b (HIB) vaccines, and 3 pneumococcal conjugate vaccines (PCV-13) as fully immunized. We will ask the primary caregiver to complete a release of medical information (for immunization records only) upon enrollment. We will obtain immunization records by sending the release to the primary care pediatrician or, when applicable, from the DC or Maryland immunization registry, which is available to Children's National health care providers with a password.

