- Developmental testing between 12-15 months of age (or around 1 year corrected age if born prematurely). We will share the results with parents and pediatrician upon participant's request. Scores for five developmental domains (cognitive, language, motor, social-emotional and adaptive/behavioral) and the composite score for the Bayley Scales for Infant and Toddler Development TM, Third Edition (Bayley-III)(Pearson Educational) will be compared. Patients will be assessed in Developmental Clinic by [name] and her team. At the end of the assessment parents will be provided with immediate feedback and suggestions for ways to help the baby at home. A brief letter is sent to the pediatrician with copy to the family (and medical record). The full time for the assessment is about an hour. The parent is present, and the baby sits on parent's lap. [name] staff will set up the appointment when they are enrolled in the study and then have the study coordinator help with reminders. Parents can change the day/time to make it suit their own schedule. If needed, we will provide testing on Saturday to accommodate parents' schedules and to reduce burden.

If a participant has already had the Bayley-III administered at CNMC within the participant's designated study window, the data will be used, and family will qualify for a gift card.

Additionally, infant's medical records will be reviewed at baseline and at 12 months. See Data collection sheet in Documents section.

Description of Intervention:

Care notebook: All participants will be provided with a care notebook designed specifically for this study. It is an enhanced version of the resource notebook developed for use by the current parent navigators at CNMC, and is used to organize the care of medically complex children. The version of the care notebook in this study includes information important for NICU graduates, including available community resources, guidance on advocating for a child with special needs, healthcare providers and educational systems, and has sections where the parent or a healthcare provider can include information important for the child's care (e.g., medications, appointment calendar, care plans, seizure logs, therapy goals, dietary schedules).

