Aim 2a. and 2.b. will compare measures of anxiety using the STAI, and depression using the CES-D in primary caregivers from the intervention and control groups. The independent variable will be the intervention group in both models. If necessary, the models will include covariates known to impact parental depression and anxiety (if different between the groups) and stratification variables. We will estimate and compare the covariate adjusted mean difference in the scores between the intervention groups using GEE models as described above (Aim 1). The difference will be considered to be statistically significant if the 95% CI around the difference fails to include 0.

As in Aim 1, group-by time-interaction models will be used to evaluate differences between the groups over time.

Aim 3. The NICU graduates may experience multiple ED visits or hospitalizations any time after baseline. The number of ED or hospitalization counts will be summed for each of the intervention groups. To assess differences between the intervention groups for each of the outcomes (ED visits or hospitalizations), we will use the Wilcoxon–Mann–Whitney two-sample rank-sum test, which is appropriate for use with nonparametric data, such as the count data from this aim. We will define the outcome, improved immunization status, as receipt of two diphtheria-tetanus-acellular pertussis (DTaP) vaccines, two Hemophilus influenzae b (HIB) vaccines, and two pneumococcal conjugate vaccines (PCV-13) by the end of the observation period (12 months after baseline). This binary outcome will be contrasted using an unpaired t-test with unequal variances to measure the hypothesis that the intervention results in improved immunization status.

Sensitivity Analyses. In sensitivity analyses, we will explore the effect of departures from assumptions made for the main analysis. A key assumption in our analyses is that missing data are missing at random, and groups who are and are not lost to follow-up are similar. We will compare characteristics of families who are, and are not, lost to follow-up. If significant differences between these two ($p < 0.05$) are observed, we can test for intervention effects, but with the assumption that individuals with missing data have worse outcomes. We will then report these ‘worst case’ scenarios and report any changes in the clinical interpretation of the trial.

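### The Protocol's immunization window (NICU discharge to 12 months of age) can score fully vaccinated infants as not immunized, and it conflicts with the Aim 3 rule in the Protocol and SAP

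*Protocol*

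**What the plan says.** The immunization outcome for hypothesis 3c is defined in two ways.

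- **Protocol, Infant health outcomes, Immunization status.** The window is given as "We will use receipt of vaccines between NICU discharge and 12 months of age as the outcome measure". The next sentence takes "receipt of 3 diphtheria-tetanus acellular pertussis (DTaP) vaccines, 3 Hemophilus influenzae b (HIB) vaccines, and 3 pneumococcal conjugate vaccines (PCV-13) as fully immunized".
- **Protocol, Statistical Considerations, Aim 3, repeated in the SAP under the same heading.** Improved status is "receipt of two diphtheria-tetanus-acellular pertussis (DTaP) vaccines, two Hemophilus influenzae b (HIB) vaccines" and two PCV-13 vaccines, "by the end of the observation period (12 months after baseline"). No opening date is given.

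Three other statements in the Protocol matter here.

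- On timing, "the baseline interview will be conducted in person while the infant is still in the NICU" (Study Design and Data Collection), and "Research study staff will approach parents anticipating discharge within 1-2 weeks" (Research Design and Methods). Twelve months after baseline therefore falls roughly 12 months after discharge, whatever the infant's age.
- On population, "we will enroll all patients discharged from the CNMC NICU" (Research Design and Methods). The eligibility criteria set no upper limit on length of stay or age at discharge.
- On data sources, vaccine records come from the pediatrician or from the DC or Maryland registry. Separately, the infant's "medical records will be reviewed at baseline and at 12 months".

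Neither document says how doses given in the NICU are credited, or how an infant discharged near or after 12 months of age is scored.

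**The concern.** The outcome-section window opens at an event that differs between infants and closes at a fixed age. Its length is 12 months minus age at discharge. Doses given in hospital fall outside it, yet they reduce the number the infant still needs. An infant can therefore have a complete vaccine record and still fail the endpoint.

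The design makes such infants plausible: a Level IV unit that takes complex cases, a stratum at or below 1500 g, and no cap on length of stay. For them the endpoint would partly reflect how long they stayed in the NICU, when hypothesis 3c is about preventive care after discharge. Failures of this kind lower apparent coverage in both arms, shrink the difference between arms and cost power.

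Because the Aim 3 text gives a different count and a different window, two analysts following the documents could classify the same infant differently.

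**Working it through.** The documents give no coverage rate, target difference or power for immunization, so there is no planned figure to reproduce. Two checks were made. All dose ages below are assumptions for scoring only, because the documents contain no vaccine schedule.

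**1. Scoring hypothetical infants under each rule**

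Scenario A: each infant receives exactly three doses of each vaccine, at 2, 4 and 6 months of age. Let d be age at discharge in months. Doses in the outcome-section window are those at age x with d ≤ x ≤ 12. Doses under the Aim 3 rule are those with x ≤ d + 12, taking baseline as approximately discharge.

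| d (months) | Doses in outcome-section window | Three-dose count, that window | Two-dose count, that window | Aim 3 rule (two doses, no opening date) |
|---|---|---|---|---|
| 0.5 to 1 | 3 | met | met | met |
| 2.5 to 3 | 2 | not met | met | met |
| 4.5 to 5 | 1 | not met | not met | met |
| 6.5 to 13 | 0 | not met | not met | met |

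Every infant in the table has all three doses, so the differences come only from the rule.

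Scenario B: no doses before discharge, then doses at d+1, d+3 and d+5.

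- d = 7: doses at 8, 10 and 12 months. Three fall by 12 months of age, so the three-dose count is met.
- d = 8: doses at 9, 11 and 13 months. Two fall by 12 months of age, so it is not met.
- d = 10: doses at 11, 13 and 15 months. One falls by 12 months of age, so it is not met.
- The Aim 3 rule is met in each case, because d + 5 is earlier than d + 12.

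**2. Illustrative cost in power, under the three-dose count**

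The sample size of 150 per arm is from the Protocol. Assumed inputs are two-sided alpha 0.05, true completion of 80% v 90%, and a share q in each arm, unrelated to completion, that cannot reach the count because of pre-discharge doses.

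Observed rate = true rate × (1 − q).

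Power = Φ( |p1 − p2| / √[p1(1−p1)/150 + p2(1−p2)/150] − 1.96 ).

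The unpooled variance corresponds to the unequal-variance t-test named under Aim 3.

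| q | Observed rates | Difference / SE | Power |
|---|---|---|---|
| 0 | 80% v 90% | 0.10 / 0.0408 = 2.45 | 69% |
| 10% | 72% v 81% | 0.09 / 0.0487 = 1.85 | 46% |
| 20% | 64% v 72% | 0.08 / 0.0537 = 1.49 | 32% |
| 30% | 56% v 63% | 0.07 / 0.0565 = 1.24 | 24% |

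A separate calculation with pooled variance under the null gives 68%, 45%, 32% and 23%. With assumed true rates of 70% v 85%, the pooled version gives 88%, 72%, 57% and 45%.

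**The case against.** The strongest reply is that the Aim 3 text, which governs the analysis in both documents, does not contain the restrictive window. It sets no opening date and closes about 12 months after discharge. Every infant in Scenarios A and B passes under it. This stands: a reader might infer that infants vaccinated in the NICU will be scored under-immunized, but the documents support that only if the outcome-section window is the one applied. Nothing says which definition prevails, so the reply narrows the point without removing it.

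A second reply is that the sentence giving the three-dose count carries no dates, and that pediatrician and registry records are not confined to post-discharge doses. A cumulative reading is possible. The window sentence comes directly before it, however, and is stated as the outcome measure, so the strict reading is at least as natural.

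Three further inferences go too far.

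- **That the window problem is wholly separate from the dose count.** In Scenario A an infant discharged at 2.5 to 3 months fails a three-dose count but passes a two-dose count in the same window. The two issues overlap, although settling the count alone would not help infants discharged from about 4.5 months onward. The power series depends on the three-dose count; under two doses the affected share would be smaller.
- **That navigation cannot influence the result in long-stay infants.** In Scenario B, late discharge with prompt catch-up still meets the three-dose count up to discharge at 7 months of age, and prompt catch-up is something navigation might affect.
- **That the comparison is biased toward one arm.** Pre-discharge doses and age at discharge should be similar between arms under randomization stratified by birth weight.

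Finally, the documents give no length of stay, in-NICU vaccination rate or coverage. The affected share is unknown.

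**Conclusion.** The point holds in a limited form. The two definitions conflict on dose count, window start and window end. If the outcome-section window is used, fully vaccinated infants with in-NICU doses can be scored as failures, and late-discharged infants have a short or empty window. Under the Aim 3 rule the same infants can pass.

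The expected consequence is dilution and lost power for hypothesis 3c. Its size cannot be fixed from the documents. The fall from about 69% to between 46% and 24% illustrates shares of 10% to 30%, and rests on the assumed rates and the three-dose count. It is not an estimate for this trial. The matter should be settled before analysis because it concerns a named hypothesis and is cheap to put right.

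**What to change.** Reconcile the Immunization status paragraph of the Protocol with the Aim 3 text of the Protocol and the SAP, so that all three places carry the same dose count and the same window. Which count applies is for the sponsor to settle.

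For the window:

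- Drop the opening at NICU discharge. Count all documented doses from birth, including those given in the NICU.
- Close at one stated end point, worded identically in all three places and defined so that late-discharged infants keep the full follow-up. The 12 months after baseline already used under Aim 3 would serve. A cut-off at a fixed age would leave those infants with a short window.
- Take doses from the planned baseline and 12-month chart reviews together with the pediatrician or registry record. The baseline review alone would miss doses given between baseline and discharge.

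The cost is a wording change plus, if not already present, a vaccine entry on the chart-review form. That form is not among the documents, so this could not be checked. The downside is that some counted doses precede the post-discharge period and cannot reflect navigation after discharge. In expectation this applies equally to both arms.

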**GPS (Giving Parents Support): Parent Navigation After NICU Discharge**

**NCT02743472**

**Statistical Analysis Plan**

**Updated/approved by Children's National IRB: 2/15/17**

**PI: [name], MPH**

### **Statistical Considerations:**

We will conduct intent-to-treat analyses to assess effects of the PN intervention such that randomized families will be analyzed according to their assigned intervention group, regardless of departures from the randomized intervention. While it is possible that families may seek some type of parental support independently of the intervention, these potential effects may be evaluated in sensitivity analyses. Our analysis strategy will first compare baseline characteristics between the PN and control groups to evaluate the balance produced by randomization. It is expected that randomization with stratification on one key confounder of birth weight ( $\leq 1500$  grams or  $>1500$  grams) will result in a balanced distribution of factors between the PN and care resource groups on most, if not all factors. However, even with randomization some imbalance may occur on a few factors and it is important to identify such factors, as these are the ones that need to be controlled during analysis.

Aim 1a. and 1b. The outcome measures involved in this aim (e.g., parenting self-efficacy measured using the PMP S-E and perceived stress scale), are derived from multi-item scales and will be treated as continuous measurements. For each scale, the mean score after baseline will be assessed at each of the visits (1 week, 1 month, 3 months, 6 months and 12 months). The overall mean difference from baseline for each of the scales between the two intervention groups will be used to evaluate Aim 1. We will assess the overall change in scores for the self-efficacy and depression scales, i.e. the population averaged effect of the intervention on changes in self-efficacy and depression, using a generalized estimating equation (GEE) model to account for the correlation between the repeated change measurements among primary care givers. The GEE model is reasonably robust to missing data. We will use an exchangeable correlation structure, but in sensitivity analyses, will also test unstructured correlation and compare parameter estimates. The main independent variable in these analyses is intervention group, however we will also include (if necessary) a cross-product term of group-by-time which will enable us to estimate differences between the intervention groups over time. The group-by-time term will be included only if it is statistically significant. The model will include covariates reflecting the randomization stratification variables, and other covariates only if imbalances are observed in the randomization groups at baseline. In addition, we will use the model to plot the change in parental self-efficacy or parenting stress over time-by-group with 95% CI around each time point estimate. The degree of change at 3-months will allow us to assess the rapidity of any effect of intervention and a descriptive comparison of the differences between the groups at 6- and 12-months will allow us to assess the degree of persistence of any effect. We will consider the difference between groups to be statistically significant when the 95% confidence intervals around the difference do not include 0.

Aim 2a. and 2.b. will compare measures of anxiety using the STAI, and depression using the CES-D in primary caregivers from the intervention and control groups. The independent variable will be the intervention group in both models. If necessary, the models will include covariates known to impact parental depression and anxiety (if different between the groups) and stratification variables. We will estimate and compare the covariate adjusted mean difference in the scores between the intervention

groups using GEE models as described above (Aim 1). The difference will be considered to be statistically significant if the 95% CI around the difference fails to include 0.

As in Aim 1, group-by time-interaction models will be used to evaluate differences between the groups over time.

Aim 3. The NICU graduates may experience multiple ED visits or hospitalizations any time after baseline. The number of ED or hospitalization counts will be summed for each of the intervention groups. To assess differences between the intervention groups for each of the outcomes (ED visits or hospitalizations), we will use the Wilcoxon–Mann–Whitney two-sample rank-sum test, which is appropriate for use with nonparametric data, such as the count data from this aim. We will define the outcome, improved immunization status, as receipt of two diphtheria-tetanus-acellular pertussis (DTaP) vaccines, two Hemophilus influenzae b (HIB) vaccines, and two pneumococcal conjugate vaccines (PCV-13) by the end of the observation period (12 months after baseline). This binary outcome will be contrasted using an unpaired t-test with unequal variances to measure the hypothesis that the intervention results in improved immunization status.

Sensitivity Analyses. In sensitivity analyses, we will explore the effect of departures from assumptions made for the main analysis. A key assumption in our analyses is that missing data are missing at random, and groups who are and are not lost to follow-up are similar. We will compare characteristics of families who are, and are not, lost to follow-up. If significant differences between these two ( $p < 0.05$ ) are observed, we can test for intervention effects, but with the assumption that individuals with missing data have worse outcomes. We will then report these ‘worst case’ scenarios and report any changes in the clinical interpretation of the trial.

Sample Size & Power. We calculated power to detect projected differences between the intervention groups for the 3 primary outcomes. All computations are based on a projected sample size of 300 families of NICU infants (i.e. 300 primary care giver evaluations, and 300 NICU infant outcome evaluations) with randomization into 2 equal groups of 150, with data collected over multiple time points during the 12 months of follow-up post discharge. In Aims 1 and 2, we will have up to 5 repeated measures after baseline (1-week, 1-month, 3-months, 6-months, and 12-months), which increases our statistical power for those aims. We assumed a modest within-subject correlation of 0.50 between these repeated measures. Using Bonferroni correction, we adjusted alpha (0.05) for the number of primary outcomes,  $n=3$ . For Aim 1, we estimate that we will have excellent power (93%) to detect differences in parental self-efficacy scores as small as 0.33SD. This estimate is based on PMSPE score distributions as reported in the literature. For the main infant outcome of number of hospitalizations during the 12-month follow-up post discharge period, we estimate that we have excellent power (99%) to detect a difference of 1 in the median number of hospitalizations between the groups. Given our conservative assumptions, including modest correlation ( $r=0.5$ ) between repeated measures and Bonferroni correction for the number of primary outcomes, we believe that our sample size ensures sufficient power to measure clinically relevant differences between the intervention groups.

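### The plan relies on GEE being robust to missing data, but a GEE on change scores without baseline score can be biased under missing at random if dropout depends on earlier scores differently by arm

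*SAP*

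**What the plan says.** All references are to Statistical Considerations in the SAP; the protocol section of that name carries the same text.

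- **Model (Aim 1a and 1b).** Change from baseline is analysed "using a generalized estimating equation (GEE) model to account for the correlation between the repeated change measurements among primary care givers". Aim 2 uses the same approach. No weighting, imputation or likelihood model is mentioned.
- **Working correlation.** "We will use an exchangeable correlation structure, but in sensitivity analyses, will also test unstructured correlation and compare parameter estimates".
- **Covariates.** The stratification variable enters the Aim 1 model. Others enter only if the arms are imbalanced at baseline, so baseline score is not assured. Visit is not listed as a main effect, and group-by-time enters only if significant.
- **Defence against missing data.** "The GEE model is reasonably robust to missing data".
- **Assumption (Sensitivity Analyses).** "A key assumption in our analyses is that missing data are missing at random", joined in the same sentence to a second condition, that "groups who are and are not lost to follow-up are similar".
- **Safeguard.** Families lost and not lost are compared. If they differ at p < 0.05, "we can test for intervention effects, but with the assumption that individuals with missing data have worse outcomes".
- **Dropout.** No rate is given. The power calculation counts all 300 families.

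**The concern.** The robustness sentence credits the method with a property it does not have in general. Under missing at random, dropout may depend on scores already observed. An unweighted GEE uses that history only through its working correlation, and here the response is a change score, so the baseline value has been subtracted out rather than conditioned on.

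The design makes arm-specific dropout conceivable. Follow-up interviews are by telephone for 12 months; intervention parents have a navigator, and controls are told they have none. Whether a parent with a poor recent score remains reachable could therefore differ by arm. If it does, the parental comparisons in Aims 1 and 2 could be shifted under an assumption that the plan itself makes.

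**Working it through.** **1. The plan's own figure.** Inputs from Sample Size & Power: 150 per arm, 5 post-baseline measures, r = 0.50, difference 0.33 SD, alpha 0.05/3 = 0.0167.

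- Variance of the mean of 5 measures: (1 + 4 × 0.5)/5 = 0.6.
- Standard error of the difference: √0.6 × √(2/150) = 0.0894.
- 0.33/0.0894 = 3.69.
- Power is 90.2% at two-sided 0.0167, 94.1% at one-sided 0.0167 and 92.6% at two-sided 0.025.

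The stated 93% is reached approximately, depending on sidedness, which is not stated. It allows for no attrition, so it gives no help on dropout.

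**2. Why bias can arise with a correct correlation.** Write Y0 for the baseline score, Yt for the score at visit t, and Dt = Yt − Y0, with unit variances and every correlation equal to r = 0.5.

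- Var(Dt) = 2(1 − r) = 1 and Cov(Ds, Dt) = 1 − r = 0.5. Change scores are therefore also exchangeable with correlation 0.5, and the working structure is right.
- Cov(Dt, Y0) = r − 1 = −0.5. Parents with high baseline scores tend to change less.
- Suppose dropout depends on the last raw score, which equals Y0 plus the last change. Given the observed changes, it still depends on Y0, which the model does not contain.
- If low scorers leave the control arm, the retained controls have higher baselines and smaller changes. On a scale where higher is better, that favours Parent Navigation. If the arms share one mechanism, the shifts cancel.

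**3. Size by simulation.** Assumptions, not document figures: no true effect; monotone dropout, possible before the 1-week interview; log-odds of dropout 1 per SD of the last raw score; visit in the model. Results are for 150 per arm, 1,000 runs, judged by the plan's 95% CI rule.

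| Dropout | True correlation | Bias (SD) | False positives | Coverage |
|---|---|---|---|---|
| None | exchangeable 0.5 | 0.001 | 6.2% | 93.8% |
| Differs by arm only, 30% setting | exchangeable 0.5 | 0.002 | 4.4% | 95.6% |
| Same mechanism, 20% | exchangeable 0.5 | 0.000 | 5.2% | 94.8% |
| Control only, 20% | exchangeable 0.5 | 0.043 | 7.9% | 92.1% |
| Control only, 30% | exchangeable 0.5 | 0.063 | 9.9% | 90.1% |
| Opposite by arm, 20% | exchangeable 0.5 | 0.070 | 13.9% | 86.1% |
| Opposite by arm, 30% | exchangeable 0.5 | 0.107 | 22.2% | 77.8% |
| Opposite by arm, 30% | AR(1) 0.75 | 0.107 | 18.8% | 81.2% |

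- Large-sample runs at 10/20/30% loss gave about 0.02/0.04/0.06 SD (control only) and 0.03/0.07/0.10 SD (opposite). The highest values were 0.07 and 0.12.
- Separate runs at about 30% loss gave 0.02-0.05 SD (control only) and 0.05-0.10 SD (opposite). With nobody lost before the 1-week interview, bias is about half as large.
- When dropout followed the last change score in opposite directions, bias was −0.002 to −0.007 SD under exchangeable correlation and −0.01 to −0.04 SD under decaying correlation.
- A likelihood-type estimator that includes baseline had bias of at most 0.006 SD in the large-sample runs. The same GEE with baseline score added had at most 0.012 SD, with false positives of 4-7%.

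**4. Do the planned checks catch it?**

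- *Unstructured correlation.* At r = 0.5, exchangeable and unstructured GEE gave the same biased value (0.090 and 0.090). With declining correlation, unstructured reduced the bias from 0.13 to 0.08.
- *Lost versus retained.* The comparison is not split by arm. Tested on baseline score, it fired in 5-6% of runs with opposite mechanisms, which is chance level. With control-only dependence it fired in 73-80%, but it leads only to an optional worst-case analysis.

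**The case against.** The strongest reply is that the bias needs a specific pattern that the documents do not predict. Several stronger readings are tempting, and the reply defeats each of them.

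- *Unequal dropout rates between arms are enough to bias the result.* They are not. With up to 13% versus 46% missing by arm alone, bias was 0.000 to 0.004 SD with visit in the model. It was −0.01 to −0.05 SD if visit was omitted and scores drifted by 0.15 SD per visit.
- *GEE requires missing completely at random.* That is too strong. Dropout explained by modelled covariates is allowed, and step 3 shows near-zero bias for dropout on change scores when the correlation is right.
- *The exchangeable structure is the culprit.* It is not the main one. In the opposite-mechanism case, bias is about the same whether the true correlation is exchangeable or declining.
- *The plan has no missing-data safeguard.* It has two checks. The clause on similarity of lost and retained groups also brings its assumption closer to missing completely at random, which softens the conflict with the method.

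It is also fair to say that replacing the main model is more than these scenarios require, because adding baseline score nearly removes the bias. What stands is narrower. The plan names missing at random, its model does not deliver validity under it, and the checks do not repair the estimate.

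**Conclusion.** The concern holds in a limited form: the Aim 1 and Aim 2 effects *can* be biased if dropout depends on earlier scores and does so differently by arm. The documents do not show that this will happen.

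At an assumed 10-30% loss, the bias is about 0.02-0.06 SD with control-only dependence, or 6-18% of the 0.33 SD target (0.02/0.33 to 0.06/0.33). False positives are then about 7-10%. With opposite mechanisms it is about 0.03-0.10 SD, or 9-30% of the target, with false positives up to about 20%. The upper figures need both about 30% loss and opposite mechanisms. The theory is firm. The size rests on assumed rates, on dropout following the raw score, and on loss starting before the 1-week interview.

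The plan also states two missing-data assumptions of different strength in one sentence and should choose one.

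**What to change.** - **Minimal change.** Always include baseline score, visit and birth-weight stratum in the Aim 1 and Aim 2 GEE models, whether or not the arms look imbalanced. This removed nearly all the bias in the scenarios above. It does not make an unweighted GEE valid under missing at random in general.
- **Preferred.** Fit a likelihood-based repeated-measures model with baseline score, stratum, visit, arm-by-visit and unstructured covariance, and estimate the average post-baseline difference between arms. GEE after multiple imputation, or with inverse-probability-of-dropout weights, is an alternative.
- **Wording.** Delete the robustness sentence and state one missing-data assumption.
- **Sensitivity analysis.** Make it unconditional rather than dependent on a p-value, and report loss by arm.

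The cost is SAP wording and slightly more analysis work with standard software; no new data are needed. The likelihood model adds a normality assumption for the scale scores and more covariance parameters.
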